1.4 Schedule of Spirometry and In-Clinic Dosing with Blinded Study Medication

Table 4: Schedule of Spirometry and In-Clinic Dosing with Blinded Study Medication

| Every effort should be made to initiate spirometry according to these timings: | Visit 1 Randomization | Week 6 Visit 2 | Week 12 Visit 3 | Week 24 Visit 5 | Early Term/Withdrawal |
|---|---|---|---|---|---|
| Pre-Dose Spirometry | Two separate timepoints within 40 minutes prior to dosing. | Within 40 minutes prior to dosing AND between 11.5 and 12 hours after the patients evening dose the day prior to this visit. | Within 40 minutes prior to dosing AND between 11.5 and 12 hours after the patients evening dose the day prior to this visit. | Within 40 minutes prior to dosing AND between 11.5 and 12 hours after the patients evening dose the day prior to this visit. | Within 40 minutes prior to dosing AND between 11.5 and 12 hours after the patients evening dose the day prior to this visit (if applicable). |
| Morning Blinded Study Medication Dosing in the Clinic | Time: Between 6 AM and 10 AM | Time: Between 6 AM and 10 AM | Time: Between 6 AM and 10 AM | Time: Between 6 AM and 10 AM | Time: Between 6 AM and 10 AM |
| Post-Dose Serial Spirometry | 30 min, 1, 2, and 4 hours post-dose. | 30 min, 1, 2, and 4 hours post-dose. | 30 min, 1, 2, 4, 6, 8 hours and the 12 hour post-dose spirometry should not start prior to 11.5 hours. | 30 min, 1, 2, and 4 hours post-dose. | 30 min, 1, 2, 4, 6, 8 hours and the 12 hour post-dose spirometry should not start prior to 11.5 hours. |
| Evening Blinded Study Medication Dosing¹ | None | None | Time: After completion of the 12-hour spirometry and between 6 PM and 10 PM | None | None |

Note: Additional details on information contained in this table can be found in Section 6.0 and Section 8.3.1. For pre-dose spirometry conducted between 11.5 and 12 hours after the patients evening dose the day prior to the visit, the paper diary with the evening dosing completion time should be consulted.

¹Patients may be discharged from the clinic after Week 12 assessments are complete to self-administer their evening dose of study medication. If administered in the clinic, the Week 12 evening dose must be administered by unblinded site staff.

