5.1 Inclusion Criteria

Informed Consent

1. Capable of giving informed consent indicating that they understand the purpose of the study and study procedures and agree to comply with the requirements and restrictions listed in the informed consent form (ICF) and in this protocol.

Age and Sex

2. Age: Patient must be 40 to 80 years of age inclusive, at the time of Screening.
 3. Sex:
 - Males are eligible to participate if they agree to use contraception as described in the contraceptive guidance (Section 11.8) from Screening and throughout the study and for at least 30 days after the last dose of blinded study medication.
 - Females are eligible to participate if they are not pregnant, not breastfeeding, and at least one of the following conditions apply:
 - a) Not a woman of childbearing potential (WOCBP) as defined in Section 11.8.
- Or
- b) A WOCBP who agrees to follow the contraceptive guidance in Section 11.8 from Screening and throughout the study and for at least 30 days after the last dose of blinded study medication.

Smoking History

4. Smoking History: Current or former cigarette smokers with a history of cigarette smoking ≥ 10 pack years at Screening (Visit 0) [number of pack years = (number of cigarettes per day / 20) \times number of years smoked (eg, 20 cigarettes per day for 10 years, or 10 cigarettes per day for 20 years)]. Pipe and/or cigar use cannot be used to calculate pack-year history. Former smokers are defined as those who have stopped smoking for at least 6 months prior to Visit 0. Smoking cessation programs are permitted during the study.

COPD Diagnosis, Symptoms, Severity and Maintenance Therapy

5. COPD Diagnosis: Patients with an established clinical history of COPD as defined by the American Thoracic Society (ATS)/European Respiratory Society (ERS) guidelines (Celli BR, 2004) with symptoms compatible with COPD.
6. COPD Symptoms: A score of ≥ 2 on the Modified Medical Research Council (mMRC) Dyspnea Scale.

7. COPD Severity:
 - a. Pre- and Post-albuterol/salbutamol FEV₁/FVC ratio of <0.70.
 - b. Post-albuterol/salbutamol FEV₁ ≥30 % and ≤70% of predicted normal calculated using the National Health and Nutrition Examination Survey III (Hankinson, 1999).

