8.3.1.1 Spirometry Training

Prior to the first spirometry measurement at each clinic visit requiring Spirometry, the site staff will train each patient on how to perform acceptable spirometry maneuvers according to instructions provided by the central spirometry vendor.

8.3.1.2 Spirometry must be performed as follows:

- **Coordination of the timing of spirometry and in-clinic dosing with blinded study medication is critical. See Section 1.4, for the Schedule of Spirometry and In-Clinic Dosing with Blinded Study Medication.**
- Spirometry Start Time: between 06:00 am and 10:00 am.
- Health Outcomes: Complete health outcome assessments as described in Section 8.3.3 prior to spirometry.
- Withhold the Following or Reschedule the Visit*:
 - *Blinded Study Medication*: Blinded study medication must be withheld until pre-dose spirometry is completed.
 - *Rescue Medication*: Albuterol/salbutamol must be withheld for ≥ 4 hours.
 - *Maintenance LAMA or LABA medications (or LAMA/ICS or LABA/ICS, if applicable)*: Must withhold Twice-Daily medications for 24 hours and Once-Daily medications for 48 hours prior to spirometry.

****If the withholding periods above are not met, the visit should be rescheduled to be held within 3 days of the scheduled visit.***

- Recommendation/ Request: Patients should refrain from smoking and/or caffeinated beverages prior to Spirometry and ECGs for the withholding periods below:
 - *Smoking*: No smoking for at least 1-hour prior to each spirometry assessment.
 - *Caffeinated Beverages*: Abstain from drinking beverages with high levels of caffeine (eg, tea, coffee) for 2 hours prior to each spirometry assessment.

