9.0 STATISTICAL CONSIDERATIONS

9.1 Statistical Hypotheses

The aim of this study is to show superiority of ensifentrine over placebo regarding selected efficacy measures. The null hypothesis to be tested for each endpoint will be that there is no difference between ensifentrine and placebo, against the alternative hypothesis that ensifentrine is better than placebo. All tests will be two-sided at a 5% significance level. Primary and key secondary endpoints used for claims will be tested in a sequential order to preserve the alpha level. Testing will stop once a not significant result is achieved. Test order will be FEV₁ AUC_{0-12h} at 12 weeks, peak FEV₁ at 12 weeks, weekly mean E-RS total symptom score at week 24, SGRQ total score at Week 24, morning trough FEV₁ at Week 12, FEV₁ AUC_{0-4h} at 12 weeks and proportion of SGRQ responders at 24 weeks.

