9.2 Sample Size Determination

Approximately 800 patients will be randomized. The standard deviation for the change in FEV₁ AUC_{0-12h} is estimated to be 250 mL. With a 2-sided test at a 5% significance level and 500 vs. 300 evaluable patients in the two groups, there will be an 90% power to detect a true difference of 59 mL between the treatments. If the withdrawal rate at 24 weeks exceeds 25% overall, additional patients may be randomized to the study to compensate for the loss of data.

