16.1.3. PRIMARY ANALYSIS OF PRIMARY EFFICACY VARIABLE

The primary objective of this study is to test the hypothesis that there is a difference between ensifentrine in comparison with placebo.

The change from baseline FEV₁ to average FEV₁ AUC_{0-12h} will be compared between ensifentrine and placebo using ANCOVA with fixed effects for treatment, region, background medication strata and smoking strata and baseline FEV₁ as covariate. Missing data will be imputed using imputation described in section 16.1.2 of the SAP. The estimated treatment difference will be presented with 95% CI and associated p-value. Furthermore, SD will be presented for the treatment difference to check the sample size with 90% power. Summary statistics will be performed on the imputed values.

Model assumptions will be tested as per the following rules on the blinded data, before the DBL.

1. Residual vs Predicted plots will be created to check residuals are uncorrelated and normally distributed.
2. Normality of the data will be checked using Kolmogorov-Smirnov normality test.

If any of the checks specified above fail the test, then alternative approaches will be discussed, including different ways of transposing data. The SAP will be updated to reflect any changes prior to DBL.

Only spirometry measurements with best test review (BTR) grades “Acceptable” and “Borderline Acceptable” are used in the analysis and baseline calculations.

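### Screening pre-bronchodilator FEV₁ is collected on every patient but not used as a covariate; adding it to the FEV₁ models is a nearly free improvement of uncertain size

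*Protocol*

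**What the plan says.** - **Baseline.** SAP 6.2 and 16.1.1.1 define baseline FEV₁ as the mean of the two pre-dose measurements on Day 1. Protocol 1.4 (Table 4) places them at "Two separate timepoints within 40 minutes prior to dosing", so both come from one morning.
- **Model.** SAP 16.1.3 specifies "ANCOVA with fixed effects for treatment, region, background medication strata and smoking strata and baseline" FEV₁ as the covariate. Protocol 9.4.1 lists the same terms. SAP 16.2.3.1 carries the approach over to peak FEV₁, morning and evening trough and AUC₀₋₄ₕ.
- **Imputation.** The primary model (SAP 16.1.2) uses treatment, region, the two strata, Day 1 baseline and the Week 12 outcome. SAP 16.2.2.1 adds the other scheduled post-baseline visits for the secondary endpoints. Neither uses Screening FEV₁.
- **Screening value.** Pre-bronchodilator spirometry is done at Visit 0 (Protocol 1.3, footnote 7) and is needed for Inclusion 7a: "Pre- and Post-albuterol/salbutamol FEV₁/FVC ratio of <0.70". Protocol 8.1.8 sends Screening spirometry to Section 8.3.1, so the central over-read, the withholding rules and "Spirometry Start Time: between 06:00 am and 10:00 am" apply to it as well. SAP 10 summarises the value and SAP 10.1 uses it to derive reversibility.
- **Sample size.** Protocol 9.2: "The standard deviation for the change in FEV₁ AUC_{0-12h} is estimated to be 250 mL". Counting 500 ensifentrine and 300 placebo patients as evaluable, it states that "there will be an 90% power to detect a true difference of 59 mL between the treatments".

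**The concern.** Averaging two readings taken within 40 minutes reduces measurement error within that session. It does nothing about variation in a patient's FEV₁ from one day to another, so part of that variation stays in the ANCOVA error term. A pre-randomization reading from a different day gives a better estimate of the patient's usual level. Adjusting for it introduces no bias and uses one degree of freedom among about 800 patients. Neither document says why it is left out.

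What is at stake is precision for the primary endpoint and the FEV₁ secondaries. The 90% power in Protocol 9.2 counts all 800 planned patients as evaluable, so it contains no allowance for missing data.

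**Working it through.** **Inputs from the documents.** Two-sided 5% (Protocol 9.1: "All tests will be two-sided at a 5% significance level"); difference 59 mL, SD 250 mL, 500 vs 300 (Protocol 9.2). The Synopsis attaches the same SD to peak FEV₁, which does not alter the arithmetic. The documents do not say whether 250 mL is the raw SD of change or the ANCOVA residual SD. I take it as the residual SD; on the other reading the planned ANCOVA starts from higher power.

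**Step 1: the plan's own figure.** SE = 250 × √(1/500 + 1/300) = 18.26 mL. Power = Φ(59/18.26 − 1.96) = Φ(1.27) = 89.8%. The stated 90% reproduces.

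**Step 2: effect of a variance reduction r.** SD = 250 × √(1 − r), then as in step 1. The sample-size equivalent is 800/(1 − r) − 800.

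| r | SD (mL) | SE (mL) | Power at 59 mL | Equivalent extra patients | 95% CI half-width (mL) |
|---|---|---|---|---|---|
| 0 | 250 | 18.26 | 89.8% | 0 | 35.8 |
| 2% | 247.5 | 18.07 | 90.4% | 16 | 35.4 |
| 5% | 243.7 | 17.80 | 91.2% | 42 | 34.9 |
| 10% | 237.2 | 17.32 | 92.6% | 89 | 33.9 |
| 20% | 223.6 | 16.33 | 95.1% | 200 | 32.0 |

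With 25% of patients not evaluable (375 vs 225), power at 59 mL is 79.9% as planned and 83.9% with r = 10%.

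**Step 3: what r might be (assumptions, not in the documents).** Let T be the between-patient variance and v the variance of independent visit-to-visit noise. The rest of the 250² is treated as specific to Week 12. The variance of the patient's level is Tv/(T + v) given Day 1 alone and Tv/(2T + v) given Day 1 and Screening. So r = [Tv/(T + v) − Tv/(2T + v)] / 250².

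With a between-patient SD of 450 mL and visit noise of 80 mL, T = 202,500 and v = 6,400. The two terms are 6,204 and 3,150, so r = 3,054/62,500 = 4.9%. Other values of visit noise:

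| Visit-noise SD (mL) | 40 | 60 | 80 | 120 | 183 |
|---|---|---|---|---|---|
| r | 1.3% | 2.8% | 4.9% | 10.4% | 21.2% |

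The last column attributes essentially all of the 250 mL to visit noise: √(Tv/(T + v) + v) = 249.5 mL. Moving the between-patient SD over 300 to 600 mL changes r little, except in that column, where it runs from 16% to 23%.

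**Step 4: a case with almost no gain.** Suppose the patient's level drifts, with correlation falling by a constant factor per unit of time. With no visit noise, Screening then adds nothing once Day 1 is known, and r = 0. With correlation 0.95 per four weeks, between-patient SD 450 mL and visit noise 80 mL, residual variance goes from about 64,600 (SD 254 mL) to about 63,800, so r is about 1%.

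**Step 5: a larger true effect.** Protocol 2.2 reports 87 mL for average FEV₁ over 12 hours at Week 4 with 3 mg added to tiotropium. Power = Φ(87/18.26 − 1.96) = 99.7% as planned and 99.9% with r = 10%. At 375 vs 225 it is 98.5% and 99.2%.

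**The case against.** The strongest reply is that nothing here is wrong. ANCOVA on a two-reading baseline plus region and the stratification factors is valid, is pre-specified in both documents and delivers its stated power. That stands.

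Four further points have weight:

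- **The gain may be negligible.** Steps 3 and 4 include cases at or near zero. Screening also precedes the run-in that is meant to secure a stable regimen. Protocol 6.7.3 allows some medicines to be stopped only hours or days beforehand (ipratropium 6 hours, theophylline 48 hours). Screening FEV₁ may therefore predict Week 12 less well than a true replicate of Day 1 would.
- **59 mL is a detectable difference, not an expected effect.** At 87 mL there is little power left to gain, although that figure comes from four weeks of Phase IIb data.
- **Variability is already watched.** Protocol 9.5 monitors it blinded, and SAP 4.2 allows more patients if the SD rises or if withdrawal and missingness are high.
- **The reach in the hierarchy is limited.** E-RS and SGRQ total score are third and fourth in SAP 7.4 and gain no precision. They benefit only because the primary endpoint and peak FEV₁ are tested first.

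These points limit the size of the benefit. They give no reason to leave the covariate out, because a pre-randomization covariate costs almost nothing even when it explains little. Its collinearity with Day 1 FEV₁ does not harm the treatment estimate.

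**Conclusion.** A free improvement, not a defect. Day 1 FEV₁, from a single morning, is the only lung-function covariate, and a second untreated reading already in hand is unused. On the assumption that 250 mL is the residual SD, and with a residual variance reduction anywhere from about 0% to 20%, power at 59 mL rises from 89.8% to at most about 95%. If the true effect is near 87 mL, the practical result is a confidence interval narrower by a few millilitres at most.

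A reader might infer three stronger things that the documents do not support:

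- **That the trial is underpowered or the primary analysis flawed.** The stated power reproduces and the model is valid.
- **That the model adjusts for baseline FEV₁ alone.** It also contains region, background medication and smoking.
- **That a gain of 5% or more in variance is assured.** This would need variance components that neither document gives.

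**What to change.** Before unblinding:

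- Add Screening pre-bronchodilator FEV₁ as a second continuous covariate in SAP 16.1.3 and, for the FEV₁ endpoints, in 16.2.3.1. Other sections (symptom scores, EQ-5D-5L, biomarkers) point back to 16.1.3, so word the addition to cover FEV₁ endpoints only.
- Add it to both steps of the matching imputation models (SAP 16.1.2 and 16.2.2.1).
- Use the latest screening for rescreened patients, in line with SAP 6.3, and the spirometry grades that 16.1.3 already accepts. State a simple rule for missing or ungradable values, for example substituting the pooled mean, so that no patient is dropped for lack of a Screening value.
- Keep the definitions of baseline and of change from baseline.
- List the change in SAP 3.3, because Protocol 9.4.1 names the covariates, and align it with study RPL554-CO-301 and the pooled SAP.

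The cost is SAP wording, one model term and that alignment; no new data are needed. SAP 16.1.3 already plans blinded model checks with a possible SAP update before database lock. The added explained variance can be examined on pooled blinded data at the same time, which would replace the assumed range with an observed figure.

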2.0 INTRODUCTION

2.1 Study Rationale

Verona Pharma plc. is developing inhaled nebulized ensifentrine for the maintenance treatment of chronic obstructive pulmonary disease (COPD). RPL554-CO-302 is one of the two Phase III confirmatory studies for the inhaled nebulized ensifentrine suspension formulation in patients with COPD.

The two confirmatory studies RPL554-CO-301 and RPL554-CO-302 are planned as randomized, double-blind, parallel-group, placebo-controlled studies intended to provide replicate evidence of efficacy in terms of improvements in lung function, symptoms and quality of life and the safety of ensifentrine compared to placebo in patients with moderate to severe COPD.

RPL554-CO-301 will enroll approximately 800 patients with moderate to severe COPD in 2 subsets. The 24-week subset will enroll approximately 400 patients randomized 1:1 ensifentrine (3 mg): placebo and the 48-week subset will enroll approximately 400 patients randomized 3:1 in order to minimize the number of patients assigned to placebo over 48 weeks. The assessments in each subset are identical over the first 24 weeks. The 48-week subset will continue to provide long-term safety data in this subset of patients.

Study RPL554-CO-302 is planned as a 24-week study that will enroll 800 patients and be randomized 5:3 to ensifentrine (3 mg): placebo and is otherwise identical to the first 24 weeks of RPL554-CO-301. This study will assess population PK via sparse sampling in all patients.

Both studies will assess lung function, symptoms, and quality of life over 24 weeks. Safety and tolerability will be assessed over 24 or 48 weeks.

A 3-day study was conducted where nebulized enfentrine or placebo was administered twice daily to patients with COPD as an add-on treatment to tiotropium (Spiriva®; RPL554-CO-202). In this study, statistically significant and clinically meaningful improvements in bronchodilation were seen compared to placebo. In addition, enfentrine significantly reduced residual lung volumes and increased the speed of onset of the bronchodilator effect to under 5 minutes.

In the first completed 4 week dose-ranging, 403-patient Phase IIb study, RPL554-CO-203, four dose levels of nebulized enfentrine (0.75, 1.5, 3, and 6 mg) were administered twice daily to patients with moderate to severe COPD not taking additional maintenance bronchodilator therapies. All doses of enfentrine met the primary endpoint, showing a statistically significant increase in peak FEV₁ vs placebo (p<0.001) with placebo-corrected changes from baseline >200 mL in peak FEV₁ after 4 weeks of dosing. In addition, statistically significant improvements in average FEV₁ over 12 hours were observed at all doses after the first administration, and this effect was sustained over 4 weeks. Notably, statistically significant and clinically meaningful improvements in total COPD symptoms were shown using the Evaluating Respiratory Symptoms in COPD (E-RS™: COPD) measure, a validated daily assessment of stable COPD symptoms. Enfentrine showed a meaningful reduction in symptoms on the total score and all subscales of the E-RS at or near the minimal clinically important difference (MCID) of each.

In a second recently completed 4 week dose-ranging, 413-patient Phase IIb study, RPL554-CO-205, with enfentrine or placebo added on to maintenance tiotropium, 4 dose levels (0.375, 0.75, 1.5, and 3 mg) of enfentrine or placebo were administered twice daily to patients with moderate to severe COPD who remained symptomatic and with impaired lung function following a 2 week tiotropium run-in. All doses of

ensifentrine met the primary endpoint, showing a statistically significant increase in peak FEV₁ (all $p < 0.05$) which was sustained over 4 weeks. For the two highest doses, 1.5 and 3 mg, increases in peak FEV₁ were observed > 100 mL compared to placebo after 4 weeks of dosing. In addition, a statistically significant and meaningful improvement in average FEV₁ over 12 hours was shown with the 3 mg dose at Week 4 (87 mL, $p = 0.0111$). Notably, statistically significant and clinically meaningful improvements in health-related quality of life as measured by St. George's Respiratory Questionnaire (SGRQ)-COPD (Meguro, 2007) were observed at Week 4 with the 1.5 and 3 mg doses of ensifentrine added onto tiotropium (placebo-corrected; both $p < 0.05$), which exceeded the MCID for both doses.

Overall, ensifentrine was well tolerated in the 15 clinical studies conducted to date, with adverse event (AE) incidence and severity generally similar to those in the placebo-treated group. Serious adverse events (SAEs) have been uncommon and there is no apparent pattern in the SAEs reported to date.

Verona Pharma is developing nebulized ensifentrine as a maintenance therapy for patients with COPD. Information on the background of ensifentrine as described in this section can be found in the Verona Pharma plc. Ensifentrine Clinical Investigators Brochure (IB) v. 20.0, 2021 (or more current version, if applicable), unless otherwise cited.

2.3 Benefit/Risk Assessment

No significant medical risks to patients have been identified from studies conducted thus far with ensifentrine administered in the solution formulation, suspension formulation, or dry powder formulation. A slight increase in mean heart rate (up to 12 beats per minute [bpm]) without reported medical significance at a 6 mg suprathreshold doses has been reported in healthy volunteers (RPL554-PK-101). In patients with COPD, transient increases in peak heart rate of 3 bpm vs placebo have been observed with the 6 mg twice daily dose only over 4 weeks. Otherwise, non-clinical and clinical data to date do not indicate any areas of particular medical safety concern.

Effects on reproductive performance in male rats given the highest dose of 15.5 mg/kg/day included lower number of pairings of dosed males resulting in pregnancy in undosed females, higher pre and post implantation loss resulting in lower mean litter size, and lower sperm motility and higher abnormal sperm. No ensifentrine-related adverse effects were observed at 5.75 mg/kg/day (20.5 times the maximum recommended human dose based on area under the curve [AUC]). There were no effects on embryo-fetal survival and development in either rats or rabbits in the main embryo-fetal development studies. Ensifentrine had no effects on fertility or reproductive performance in female rats.

Ensifentrine has statistically and clinically significant bronchodilator as well as anti-inflammatory effects. As such, the clinical development of ensifentrine is focused on the treatment of obstructive and inflammatory lung diseases, including COPD.

Considering the consistent improvements in lung function, symptoms, and health-related quality of life across multiple studies in patients with COPD and the overall favorable safety profile in studies to date, the benefit/risk profile of ensifentrine is considered positive.

More detailed information about the known and expected benefits and risks and reasonably expected AEs of ensifentrine can be found in the Verona Pharma plc. Ensifentrine Clinical IB v. 20.0, 2021 (or more current version, if applicable).

